STATISTICAL ANALYSIS PLAN

Project Title: Perioperative pregabalin as part of a multimodal treatment plan for pain after

ureteroscopy with stent placement: a pilot

IRB Number: 2013680 Version Number: 1.1 Version Date: 11/20/2019

Principal Investigator: [name]

Funding Source: Departmental Clinical Trial Phase: Not Phased

Clinicaltrials.gov Number: NCT03927781 Study Drug/Study Device: Pregabalin

Principal Investigator	[name]	Department of Surgery Urology
		Division
Co-Investigator	[name]	Department of Surgery Urology Division
Consenting Professional(s)	Donartment of Surgery	DIVISION
Consenting Professional(s)	Department of Surgery-	
Department	Urology	

University of Missouri University Hospital Department of Surgery Urology Division [name] Descriptive statistics (counts, proportions, medians) will be used to describe all data. We will describe the demographic information of the patients enrolled and the number of patients approached to meet full enrollment. We will assess the proportion who anticipated needing opioid pain medication, who appropriately received pregabalin, who received opioid pain medication at discharge, who had emergency room visits or hospitalizations in the first 30 post-operative days, and who received opioid prescriptions within the first 30 post-operative days. We will describe the number of oral morphine equivalents prescribed. We will include median USSQ scores. We will describe proportions reporting possible adverse effects and pain level reported. All analyses will be performed in R version 3.5.1. There will be no statistical tests performed.

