We propose a pilot clinical trial on the use of perioperative pregabalin in order to decrease ureteral stent related symptoms and decrease opioid usage after ureteroscopy with stent placement. Patients undergoing ureteroscopy with stent placement will receive a single dose of 300 mg pregabalin PO in the preoperative area. We will assess safety and feasibility of studying this regimen at our institution, with the aim of performing a randomized, placebo-controlled, double-blinded study in the future.

OBJECTIVES AND SCIENTIFIC AIMS

Primary Hypothesis

It is safe and feasible to study perioperative pregabalin in ureteroscopy with stent placement at our institution.

Exploratory Hypotheses

We hypothesize that the use of the perioperative pregabalin will:

- decrease ureteral stent related symptoms at 3 days post-op
- decrease the probability of a patient requiring narcotic pain medication
- decrease the total amount of narcotic pain medication used
- decrease the unplanned contact between the patient and the healthcare system related to the stent
- improve patient satisfaction after ureteroscopy with stent placement

Primary Endpoints

The primary endpoints will be as follows:

- Adverse events related to study drug
- Verified correct administration of study drug
- Correct use of study instruments

Secondary Endpoints:

Secondary endpoints include the following:

- Ureteral Stent Related Symptom Questionnaire (USSQ) [1] score at 3 days post op
- Monitored prescribing of narcotic pain medication
- Number of patients taking narcotic pain medication at several time points
- Oral morphine equivalents the patient has used at several time points
- Number of unplanned contacts between the patient and the healthcare system within 30 days
- Score on standardized evaluation of patient satisfaction

BACKGROUND AND STUDY DESIGN/INTERVENTION

The prevalence of urolithiasis is greater than 8% and increasing in the United States (US) [2]. There are several treatment options, including ureteroscopy (with or without laser lithotripsy), extracorporeal shock wave lithotripsy, and percutaneous nephrolithotomy. A recent study in California demonstrated that ureteroscopic treatment was employed in more than 40% of interventions [3], with some nationwide estimates up to 59% [4]. At least 300,000 stone

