We propose a study to extend the literature base on the use of perioperative pregabalin to ureteroscopy with stent placement through a prospective, randomized controlled trial. In order to ensure safety and feasibility of this future study, we will first perform a small pilot. We will administer study medication and study questionnaires. There will be additional components of study evaluation. This will be used to inform the design of a future trial.

CRITERIA FOR SUBJECT ELIGIBILITY

Subject Population

Undergoing elective ureteroscopy with stent placement by [name] at University of Missouri Hospital and affiliated facilities

Subject Inclusion

Age \geq 18 years

Subject Exclusion

- Renal insufficiency (eGFR $<$ 30 mL/minute/1.73 m²)
- Chronic indwelling ureteral stent
- Chronic opioid use
- History of opioid abuse
- Chronic gabapentinoid use
- Plan for inpatient hospitalization
- Pregnancy
- Inability of the patient to consent for themselves in English
- Allergy to gabapentinoid
- Liver failure or hepatic dysfunction

OVERVIEW OF STUDY DESIGNATION

Design

This is a pilot clinical trial on the use of perioperative pregabalin in order to decrease ureteral stent related symptoms and decrease opioid usage after ureteroscopy with stent placement. Patients undergoing ureteroscopy with stent placement will receive a single dose of 300 mg pregabalin PO in the preoperative area.

Pre-op standardized care

After obtaining written consent, patients will be enrolled. All patients will be told the following by a member of the study staff:

“We will be administering several medications before, during, and after your procedure to help with pain. We expect that you will be able to go home with just non-steroidal pain medication.” They will also be counseled on the risks and benefits of non-steroidal anti-inflammatory drugs (NSAIDS).

Subsequently, all patients will be given a single dose of pregabalin 300 mg PO with a sip of water approximately one hour before surgery. This will be administered per standard institutional practice. It will be recorded in the regular medical chart of the patient.

Post-op standardized care

Perioperative care, surgery and anesthesia, for all subjects will be per standard hospital protocol.

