A standardized post-operative regimen will be used, consisting of a single belladonna & opium suppository, a single dose of ketorolac 30mg IV, and ondansetron 4mg IV. A single dose of hydrocodone 5mg with acetaminophen 325mg PO will be available PRN pain.

To qualify for discharge from the PACU, all patients will have had to have met a standardized set of discharge criteria. They will have to have ambulated, voided, tolerated PO intake, and have pain subjectively adequately controlled.

On PACU discharge, patients will be given a prescription for 20 tablets of 50mg diclofenac, 20 tablets of acetaminophen 650mg to be taken on a scheduled basis every 6 hours, and mirabegron 50mg once daily PO to be taken until stent removal [15]. There is no universal standard of care discharge regimen after ureteroscopy, but a similar one to this has been shown to be safe and effective [26]. Patients will receive a standardized sheet of return precautions. They will receive packets of questionnaires to be completed along with pre-addressed and pre-stamped envelopes. They will be instructed to only seek pain medication from the urology team for the next month. Should they have need for further pain medication, patients will be instructed to call the clinic [see supplementary material]. They will be offered their choice of another 3 days of NSAID or oxycodone 5mg q6h PRN pain 6 tablets. Further treatment will be at provider discretion. The clinic staff will be instructed to record these prescriptions.

THERAPEUTIC AND DIAGNOSTIC AGENTS

Pregabalin is an oral agent approved for use in fibromyalgia and neuropathic pain. A single dose of 300mg PO will be given to all patients.

RECRUITMENT PLAN

Patients will be recruited from the practice of [name] in the Division of Urology, Department of Surgery. The study will be introduced to every eligible patient scheduled for ureteroscopy with stent placement by the participating consenting physicians from the Department of Surgery-Urology Division and a written consent obtained prior to surgery by the consenting research personnel. Candidate subjects will be provided time to consider the study, to read the informed consent document at their convenience, and discuss the study with family and others, as desired. It will be clearly indicated that non-enrollment in the study will not negatively affect the patient's care.

PRETREATMENT EVALUATION

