
- Yes
- No

On what side was ureteroscopy performed?

- Right
- Left
- Bilateral
- None

Was the patient extubated in the OR?

- Yes
- No

What was the planned disposition for the patient?

[figure not shown]
- Home from PACU
- Floor
- ICU

Pacu Discharge

At one hour post op: How much pain is the patient in?

No pain

Most pain

(Place a mark on the scale above)

Where is the patient going after PACU discharge?

- Home from PACU
- Floor
- ICU

How long was it (in minutes) from when the patient arrived in the PACU until they went home?

Please indicate if the patient experienced any of the following since surgery. A check indicates that the patient did experience this adverse event.

	Yes
Dizziness	
Vertigo	
Incoordination	
Balance disorder	
Ataxia	
Diplopia	
Blurred vision	
Amblyopia	
Tremor	
Somnolence	
Confusional state	
Disturbance of attention	
Thinking abnormality	
Euphoria	
Edema	
Peripheral edema	
Asthenia	
Fatigue	
Dry mouth	
Constipation	
Amnesia	
Back pain	
Contusion	
Depersonalization	
Diarrhea	
Fall	
Headache	
Hyperhidrosis	
Increased appetite	
Infection	
Memory impairment	
Nausea	
Nervousness	
Neuropathy	
Pain	
Paresthesia	
Sinusitis	

Upper RTI

Vomiting

What are the patient's expectations regarding post-operative pain?

- There will be minimal pain regardless of treatment
- The pain regimen being given for discharge will be sufficient
- More pain medication will be required

What pain control does the patient believe they will need in addition?

- Opioid pain medication
- Non-opioid pain medication only

Aldrete

Time to Aldrete 9 or 10:

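### The SAP's discharge opioid proportion is zero by design, while the as-needed hydrocodone dose after surgery has no staff-recorded field and no line in the SAP

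*SAP*

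**What the plan says.** **Outcome.** Among its descriptive proportions, the SAP lists patients "who received opioid pain medication at discharge". It also lists the proportion with an opioid prescription in the first 30 days, oral morphine equivalents prescribed, and pain level. No tests are planned.

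**Discharge regimen.** Protocol, Post-op standardized care: "On PACU discharge, patients will be given a prescription for 20 tablets of 50mg diclofenac, 20 tablets of acetaminophen 650mg", plus mirabegron. No opioid is included. The script in Pre-op standardized care tells every patient: "We expect that you will be able to go home with just non-steroidal pain medication". A patient who needs more is to call the clinic: "They will be offered their choice of another 3 days of NSAID or oxycodone 5mg q6h PRN pain 6 tablets".

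**Early rescue.** The same post-operative section says: "A single dose of hydrocodone 5mg with acetaminophen 325mg PO will be available PRN pain". Its place in the text, before the PACU discharge criteria, puts this dose in recovery. A belladonna and opium suppository and IV ketorolac are part of the regimen for everyone.

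**Forms.** In Appendix 1, the Pacu Discharge form asks "At one hour post op: How much pain is the patient in", then destination, time in PACU, adverse events and expectations. It has no item for analgesics given.

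**Aim.** One exploratory hypothesis is that pregabalin will "decrease the probability of a patient requiring narcotic pain medication". The secondary endpoints include patients taking narcotics, and morphine equivalents used, at time points that are not named.

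**The concern.** The intervention is one oral dose about an hour before surgery, so recovery is the window closest to it in which need for an opioid can show itself. The SAP's earliest opioid outcome is instead discharge receipt, which the regimen decides in advance. An unlabelled value at or near zero could be taken as a sign of opioid sparing and carried into planning of the randomized trial.

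The one-hour pain score is affected too. Nothing on the form shows whether the as-needed dose came before the score, so a low score after hydrocodone looks the same as a low score without it.

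This pilot exists to inform the later trial, and correct use of the study instruments is one of its primary endpoints. A gap in an instrument is the kind of thing it should find.

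**Working it through.** **1. The plan's own figure.** Protocol, Sample Size: 20 enrolled so that 10 complete. Implied attrition is 1 − 10/20 = 50%, and 10/(1 − 0.50) = 20, which agrees. This is a consistency check only. There is no power or error-rate figure to reproduce, and the point does not depend on one.

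**2. Discharge outcome under the regimen.** With full adherence, the count is 0 whatever the drug does. Exact (Clopper-Pearson) 95% upper limit for zero events: 1 − 0.025^(1/n).
- n = 10: 0/10, interval 0 to 30.8%
- n = 20: 0/20, interval 0 to 16.8%

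**3. What a non-zero count would mean.** Let d be the probability per patient that staff depart from the regimen. The documents give no value, so d is assumed. P(at least one) = 1 − (1 − d)^n.

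| d (assumed) | n = 10 | n = 20 |
|---|---|---|
| 2% | 18% | 33% |
| 5% | 40% | 64% |
| 10% | 65% | 88% |

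A non-zero result is quite possible, but it follows d and so describes departures from the regimen.

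**4. Where the as-needed hydrocodone could be recorded.**

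| Instrument | Completed by | Captures the dose? |
|---|---|---|
| Pacu Discharge | Patient/PACU nurse | No analgesic item |
| Evaluation of trial PACU nurse | Nurse | No; free comment on the study |
| Aldrete (Appendices 1 and 3) | Nurse | No; recovery score and time |
| Post-op Surgeon | Treatment staff | No |
| Early patient questionnaire, days 3 and 7 | Patient | Possibly; free-text list of pain medicines since the operation |
| 30 Days Post Op Study | Study staff | No; prescriptions |
| Unanticipated Contact | Respondent not shown in the table | No; prescriptions at later contacts |

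The one possible route depends on a patient who was recovering from general anesthesia knowing the drug and dose. It does not separate PACU from home use, and it is lost when the questionnaire is not returned.

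**5. Where the SAP could report it.** Its opioid items are discharge receipt, 30-day prescriptions and morphine equivalents prescribed. A dose administered in PACU fits none of them.

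**6. What the added outcome would give.** Each patient is 1/10 = 10 percentage points. The documents give no rescue rate, so the counts below are assumed. Exact 95% intervals:
- 2/10: 2.5 to 55.6%
- 5/10: 18.7 to 81.3%
- 8/10: 44.4 to 97.5%

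Unlike the discharge item, this proportion can move with need, but it will be imprecise.

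**The case against.** **The dose is not wholly uncaptured.** A reader might infer that the as-needed opioid appears on no study form. The documents do not support that: the Early patient questionnaire asks about all pain medicines since surgery, which covers a recovery-room dose. This objection stands, and the gap is the lack of a staff-recorded field.

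**The SAP already has need-driven outcomes.** An opioid prescription within 30 days follows from a patient calling for more relief, and staff record it. That also stands. The plan does address need after discharge. What it leaves out is the earlier, administered dose. The protocol endpoints on narcotic use could include PACU, and the SAP opens by promising description of all data, but no time point is named and no staff form would supply the value.

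**The discharge proportion is a fair feasibility result.** Whether patients do go home without an opioid is worth counting in a pilot, and departures or a floor or ICU disposition could make it non-zero. I agree it should be kept. The SAP simply does not say that this is what it measures.

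**The harm is limited.** With no control group and no tests, a count near zero cannot support an efficacy claim. That is correct, and no error rate, sample size or primary endpoint is affected.

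**Rescue is not a clean marker.** Every patient is due an opium-containing suppository, and anesthesia follows hospital standard, so other opioids may be given. This stands as a condition on the fix: a general any-opioid item for PACU would be near 100%.

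**Conclusion.** The point holds as a cheap improvement to data capture and reporting. If the protocol is followed, the discharge opioid proportion is zero by design and measures adherence. The as-needed hydrocodone dose has no staff-recorded field, is not named in the SAP, and rests on patient recall at days 3 and 7.

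A reader might go further and infer that patients given rescue would be reported as having needed no opioid. The documents do not support that. The discharge item concerns a different event, so rescue in PACU would go unreported, not be reported as zero. How many patients are involved cannot be known from the documents; each is 10 percentage points of 10 completers.

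The conclusion assumes that the as-needed dose is given before PACU discharge, as its place in the protocol implies, and that no instrument beyond those reproduced in the appendices abstracts the administration record. The copyrighted stent questionnaire is not reproduced there. Appendix 1 shows only its completion date and three index scores being entered.

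**What to change.** **Pacu Discharge form.** Add fields copied from the administration record: as-needed hydrocodone/acetaminophen given (yes/no) and clock time; any other PACU opioid and its dose. Record these separately from the belladonna and opium suppository.

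**SAP.**
- Report the proportion given the as-needed rescue opioid.
- List each patient's one-hour pain score beside whether rescue came before it. With about 10 completers, a listing is more honest than subgroup summaries.
- Describe the discharge proportion as adherence to the opioid-free discharge regimen. Keep the 30-day prescription outcomes as they are.

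**Cost.** A few chart-abstracted fields and a few SAP sentences. Care, sample size and the absence of testing do not change. The rescue proportion will be imprecise at n = 10 and should be presented as such.
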